1.3.4 Safety Studies

Two safety pharmacology studies were conducted with IMSA101 including an *in vitro* human ether-à-go-go-related gene (hERG) channel assay and *in vivo* study to evaluate cardiovascular function in monkeys. Both studies demonstrate that IMSA101 does not affect cardiovascular function in *in vitro* system and monkeys.

Organ/ Systems Evaluated	Species/ Strain	Method of Admin.	Doses (mg/kg)	No. per Group	Noteworthy Findings	GLP Compliance	Study Number
Blood pressure, ECG	Macaca fasicularis	SC	0.03, 0.30, 0.60, 0.10/1.0 ^a	10 per sex	No dose related effect	Yes	8370304
In vitro hERG	Human	In vitro incubation	0.1, 1.0, 10.0 and 100.0 μM	3 per dose level	Low potential for hERG activation	Yes	170520. DPW

Table 3	Safety Pharmacology Studies
---------	-----------------------------

ECG: electrocardiogram; GLP: good laboratory practice; hERG: human ether-à-go-go-related gene; SC: subcutaneous

^a Administration of 0.1 mg/kg of IMSA101 on Day 1. Administration of 1.0 mg/kg of IMSA101 beginning on Day 8 and weekly thereafter.

To evaluate the potential effect of IMSA101 on the cardiovascular system, safety pharmacology endpoints of blood pressure and electrocardiogram were evaluated in the good laboratory practice (GLP) monkey study (Covance study 8370304). There are no dose-related findings noted (Table 3).

The *in vitro* effects of IMSA101 on the hERG potassium channel current (a surrogate for IKr, the rapidly activating, delayed rectifier cardiac potassium current) expressed in mammalian cells was evaluated at ambient temperature using the QPatch HT[®] (Sophion Bioscience A/S, Denmark), an automatic parallel patch clamp system (Effects of Two Test Articles on Ion Channels Expressed in Mammalian Cells, hERG assay, Study No. 170520.DPW). IMSA101 was evaluated at 0.1, 1.0, 10.0 and 100.0 μ M, with each concentration tested in three cells (n = 3). The duration of exposure to each concentration was at least 3 minutes. On average, no more than 8.7% of hERG current was inhibited at concentrations up to 100 μ M; therefore, the IC₅₀ values for IMSA101 was greater than 100 μ M, indicating a low potential for hERG activation.

1.4 CLINICAL EXPERIENCE

IMSA101 has not been tested clinically.

Clinical trials of similar STING agonists are in progress. These include MIW815 from Novartis/Aduro Biotech (Aduro Biotech Inc. 2016) and MK-1454 from Merck (Merck Sharp & Dohme Corp. 2017). Early results of these studies demonstrate agonism of the STING pathway by cyclic dinucleotides similar to IMSA101. The dose-related findings are consistent with the findings seen in preclinical studies and related to the MOA of a CDN STING agonist.

1.5 SUMMARY OF KNOWN RISKS AND BENEFITS

Anticipated risks based on findings from pre-clinical studies are listed below.

Consistent with the MOA of a STING agonist, the following IMSA101-related findings in these studies were noted:

Dose-proportional Findings:

• Minimal to mildly increases in body temperature

Altered Hematology Parameters:

- Minimal to mildly variable, mild-minimal decreases in platelets, mean corpuscular volume, MCH, and hemoglobin
- Minimal to mildly variable, mild-minimal increases in absolute monocyte count, large unstained cells, eosinophils, white blood cells, RBC, hematocrits, and reticulocytes
- Increases and decreases in basophils and absolute lymphocyte count

Clinical Chemistries:

- Minimal to mildly increased in alanine aminotransferase, aspartate aminotransferase, alkaline phosphatase, gamma-glutamyl transferase, creatine kinase (CK), inorganic phosphorus, urea nitrogen, and fibrinogen
- Minimal to mildly lower creatinine, total calcium, potassium, globulin, total protein, CK, glucose, cholesterol, triglyceride, and sodium
- Minimal to mildly prolonged activated partial thromboplastin time, prothrombin time
- Increases in IL-8, TNFα, IL-6, IFNα, MCP-1, IP-10, IL-1ra

The following drug-related events were reported in ongoing clinical trials evaluating other STING agonists being studied in clinical trials:

Novartis/Aduro Biotech (MIW815) (Aduro Biotech Inc. 2016):

- Headache
- Injection site pain
- Fever
- Elevated lipase

Merck (MK-1454) (Merck Sharp & Dohme Corp. 2017):

- Vomiting
- Fever
- Injection site pain
- Headache
- Chills
- Fatigue
- Myalgia

- Tumor pain
- Diarrhea

Based on pre-clinical findings with IMSA101 and toxicity events reported in clinical trials evaluating other STING agonists, the following risks may reasonably be anticipated in clinical trials evaluating IMSA101:

- Body temperature increases (fever)
- Chills
- Alterations in serum chemistries
- Altered serum hematology parameters
- Headache
- Injection site pain
- Vomiting
- Fatigue
- Myalgia
- Diarrhea

IMSA101 Combinations:

Some patients in this study will be treated with a combination of IMSA101 and an immune checkpoint inhibitor (ICI) targeting either programmed cell death receptor-1 (PD-1) or programmed cell death-ligand 1 (PD-L1). Multiple drugs against PD-1 and PD-L1 are in development and have shown great promise across multiple cancer types. Nivolumab and pembrolizumab, both of which target PD-1, and atezolizumab, avelumab, and durvalumab, all of which target PD-L1, have been approved in various cancer types including melanoma, renal cell carcinoma, non-small cell and small cell lung cancer, head and neck cancer, urothelial cancer, Hodgkin lymphoma, Merkel cell carcinoma, as well as other solid tumors which demonstrate a high level of mutations (also known as microsatellite instability-high or mismatch repair deficient tumors). ICIs are associated with a variety of side effects termed immune-related adverse events. Believed to arise from general immunologic enhancement, these side effects can include skin, gastrointestinal, liver, endocrine/hormonal, and other less common inflammatory events. Although extremely rare, fulminant and even fatal side effects can occur with immune checkpoint inhibitors and prompt recognition and management is essential. These immune related adverse events are generally managed through interruption of the checkpoint inhibitor and temporary immunosuppression with corticosteroids and other drugs. The prescribing information and specific risks associated with particular ICIs selected by investigators will be discussed by investigators with their patients and referenced during informed consent.

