The toxicological evaluations of IMSA101 included studies in the rat and cynomolgus monkey (non-human primate [NHP]) and should be relevant to assessing potential human risk, as the STING pathway, the target of IMSA101, is conserved across species.

The non-good laboratory practice (GLP) studies in the rat and NHP covered a broad range of doses and regimens. The objective of these studies was to evaluate the effects of IMSA101 following multiple ascending doses, single doses, and multiple doses. The results of the studies provided guidance to the design of the subsequent GLP studies in the rat and NHP.

The general findings in these studies were related to the mechanism of action (MOA) of IMSA101 and can be categorized as inflammatory responses characterized by dose-related increases in STING pathway factors including Type 1 Interferons (IFNs) and proinflammatory cytokines. The findings were similar in the rat and NHP. The most consistent dose related findings were increases in IFN α , TNF α , and IL6 in the rat and monkey; IL-8 in the rat; IL-1ra, IFN γ -inducible Protein 10 (IP-10), and Monocyte Chemoattractant Protein 1 (MCP-1) in the monkey. The cytokine levels showed increases in the first 3-6 hours with return to baseline in most cases by 6-24 hours. The innate immune response is characterized by a self-regulating/modulation of the production of these factors. At low doses, the findings would be

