characterized as pharmacological changes related to the MOA of IMSA101. With increasing doses, the changes could be characterized as "exaggerated" pharmacology, which is expected changes related to the MOA of IMSA101, but greater than the responses needed to affect a therapeutic response. At the highest dose levels, the IMSA101 pharmacology and exaggerated pharmacology resulted in toxicity. Mortality was seen in the GLP rat study in the high doses group at 10 and 30 mg/kg. Test article-related increased incidence or severity of minimal or slight white matter vacuolation in the brain (within the cerebellum) was noted in animals administered ≥ 1 mg/kg IMSA101 and necropsied at a scheduled or unscheduled interval. The observations were not dose-dependent. In recovery animals, white matter vacuolation was minimal in severity and the incidence was similar between control and high dose groups. There were no abnormal clinical observations that correlated to the brain lesions. Mortality was also seen at the 3.0 mg/kg dose level in the non-GLP NHP study. The deaths were attributed to pulmonary edema consistent with an IMSA101 mediated inflammatory response that was well beyond exaggerated pharmacology and caused the severe toxicity.

The other common findings across species and across the dose ranges/regimens were doserelated findings including a range of macroscopic, hematological, clinical chemistry, and microscopic findings. At the low doses, these changes were consistent with a desired therapeutic effect; at the highest doses, there were severe toxicities and mortality. In studies with recovery animals, there was either full recovery or a trend to recovery in the parameters showing doserelated changes.

The toxicokinetic findings showed no sex related differences, dose proportionality, and no accumulation in the multiple dose studies.

Moribundity and death were seen at the mid and high dose levels in the GLP rat study. Although there was no clear cause of death, the finding was consistent with a dose-related inflammatory response, due to exaggerated pharmacology of the MOA of IMSA101. The 3000 to 10000-fold safety margins at the 10 and 30 mg/kg dose levels in the GLP rat study should reduce safety concerns related to the deaths seen in that study.

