The highest non-severely toxic dose (HNSTD) of IMSA101 was determined as 0.3 mg/kg in the monkey GLP study. The first-in-human (FIH) dose was calculated from this dose as 100 μ g. Using the minimum anticipated biological effects level (MABEL) based on mouse data, FIH dose at 100 μ g was estimated.

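### Fatal pulmonary edema seen in monkeys is missing from both risk lists (1.5 and 5.1.12), and no respiratory reading is required after any injection

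*Combined protocol and SAP*

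**What the plan says.** **Toxicology.** Section 1.3.3 reports mortality at 3.0 mg/kg in a non-GLP monkey study. On the cause it says: "The deaths were attributed to pulmonary edema consistent with an IMSA101 mediated inflammatory response". It describes this response as going well past exaggerated pharmacology. It gives no clear cause for the rat deaths, so pulmonary edema is the only fatal animal toxicity with a named cause. It also states: "The highest non-severely toxic dose (HNSTD) of IMSA101 was determined as 0.3 mg/kg in the monkey GLP study".

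**Risk lists.** Section 1.5 introduces its content with "Anticipated risks based on findings from pre-clinical studies are listed below". It then gives the animal findings (temperature, hematology, chemistry, cytokines), events reported with two other STING agonists, and ten risks to be anticipated in trials of IMSA101. Section 5.1.12 repeats those ten. Neither section names pulmonary edema, any other respiratory event, or death in animals. Section 1.4 says "IMSA101 has not been tested clinically", so by the protocol's own account animal data and related agents are the only sources for these lists.

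**Monitoring.** Vital signs are blood pressure, respiration rate, heart rate and temperature (Section 6.5). On Cycle 1 Day 1 they are recorded within the 72 hours before (Section 5.1.2; Table 1 footnote 16; Table 2 footnote 13). Sections 5.1.3 to 5.1.6 require them at later dosing visits without a time relative to the injection. Patients are observed for 1 hour after every injection and stay overnight after Cycle 1 Day 1, with no readings specified for either period.

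**The concern.** Sections 1.5 and 5.1.12 are where site staff would look to learn what to watch for. A reader who relies on them would expect fever, chills, injection-site pain and laboratory changes, and would have no prompt to watch breathing. The schedule does not make up for this, because it never requires a respiratory measurement after a dose. Vital signs may be taken whenever clinically indicated (Section 6.6), but that depends on someone suspecting a problem.

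What is at stake is early recognition of a serious lung event in individual patients, and whether comparable respiratory data exist when the Cohort Review Committee (CRC) reviews a dose level. No endpoint, analysis or sample size is affected.

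**Working it through.** **1. How far above the HNSTD the deaths occurred.** Inputs, both from Section 1.3.3: lethal level 3.0 mg/kg, HNSTD 0.3 mg/kg. Ratio = 3.0 / 0.3 = 10. This needs no scaling assumption.

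**2. How far the top planned dose (4,800 µg, Table 5) lies below the lethal level.** The protocol gives 100 µg as 1/60 of the HNSTD (Section 3.1.1; Table 5 footnote). Plain mg/kg does not reproduce that fraction: at an assumed 60 kg, 0.3 × 60 = 18 mg = 180 × 100 µg. A conversion that the text does not state must therefore be involved, and both scales are shown.

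- Protocol's 1/60 scale: HNSTD = 60 × 100 = 6,000 µg; lethal level = 10 × 6,000 = 60,000 µg; 60,000 / 4,800 = 12.5.
- Plain mg/kg, assumed body weight 50, 60 and 80 kg: 3.0 × 50 / 4.8 = 31.3; 3.0 × 60 / 4.8 = 37.5; 3.0 × 80 / 4.8 = 50.

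The top dose is thus 12.5-fold, or about 31- to 50-fold, below the level at which monkeys died.

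**3. What respiratory reading is required after each dose.**

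| Dose | Required vital signs | Time already on site after the dose | Required post-dose respiratory reading |
|---|---|---|---|
| Cycle 1 Day 1 | Within the 72 h before | 1 h, overnight; Phase I cytokine draws at 2, 4, 6 and 24 h | None |
| Cycle 1 Days 8 and 15 | At the visit, time not set | 1 h | None |
| Cycle 2 onward, Days 1 and 15 | At the visit, time not set | 1 h; Phase I draws at 2, 4, 6 and 24 h on Cycle 2 Day 15 only | None |

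The order of items in the visit lists does not settle the timing. Section 5.1.3, for example, lists the post-dose ECG ahead of the injection, so the lists are not chronological.

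**4. Where full doses fall.** In the primed combination cohorts the first full dose is on Day 8 (Section 3.1.1). The Day 1 priming dose is 1,200/2,400 = 50%, 2,400/3,600 = 67% and 3,600/4,800 = 75% of the full dose. At the de-escalated levels it is 1,200/1,800 = 67%, 2,400/3,000 = 80% and 3,600/4,200 = 86%. Any Cohort Xa in monotherapy also starts with a reduced Day 1 dose. In all of these the overnight stay follows the smaller dose, and the first full dose is followed by 1 hour of observation.

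**The case against.** The strongest reply is that nothing is concealed. Section 1.3.3 gives the deaths, the dose, the cause and the mechanism, and the Investigator's Brochure, which is not among these documents, may list them too. That stands: this is an omission from two lists, and a reader who infers that the protocol hides the finding is mistaken.

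A second reply is that the ten-item list covers what may reasonably be anticipated, and deaths at 10 times the HNSTD in a non-GLP study need not qualify. That is a defensible scope for the ten items. It does not fit the opening sentence of Section 1.5, which promises risks based on pre-clinical findings without that limit.

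Third, the safeguards are substantial: overnight stay, 1-hour observation, a two-week stagger after the first patient, a 28-day wait and CRC review before escalation, and combination dosing only after two monotherapy levels are confirmed safe. Related non-hematologic events of Grade 3 or higher in Cycle 1 count as dose-limiting, with exceptions for gastrointestinal events and fatigue. Vital signs may be taken when clinically indicated. These lower the risk and argue against a high rating, but none requires a respiratory reading.

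Fourth, an added reading may come at the wrong time. Section 1.3.3 says of the animals: "The cytokine levels showed increases in the first 3-6 hours with return to baseline in most cases by 6-24 hours". A reader might infer that edema would follow the same clock and that a 1-hour reading would miss it. The documents give no time to onset of edema, so they show neither that the 1-hour reading would detect it nor that it would miss it.

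**Conclusion.** The concern holds as a modest, inexpensive safety improvement. Pulmonary edema is absent from both risk lists although Section 1.3.3 names it as the cause of death in monkeys at 10 times the HNSTD, and no post-dose respiratory reading is required after any injection. Both statements rest on the text alone. Only the plain mg/kg multiples in the working depend on an assumed body weight (50 to 80 kg).

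Some stronger readings are not supported:

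- **That the planned doses are unsafe.** The top dose is 12.5-fold below the lethal monkey level on the protocol's scale and about 31- to 50-fold below it on plain mg/kg. Nothing here calls for a dose change.
- **That the widely spaced cytokine draws are a gap in safety monitoring.** They are exploratory samples analysed centrally (Sections 2.4.5 and 6.8.1). They matter here only because the patient is on site. Likewise, the fixed post-dose time for the ECG is no defect.
- **That the rat safety margin is wrong.** Section 1.3.3 says: "The 3000 to 10000-fold safety margins at the 10 and 30 mg/kg dose levels in the GLP rat study should reduce safety concerns". It states no human dose or basis, so the figure cannot be checked, but that does not show an error. No dosing decision uses it: Section 1.3.3 derives the starting dose from the monkey HNSTD and also cites a minimum anticipated biological effect level from mouse data.

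**What to change.** 1. Add to Sections 1.5 and 5.1.12 a line such as: *fatal pulmonary edema in monkeys at 3.0 mg/kg (10 times the HNSTD)*.
2. Record respiration rate and SpO2 before each injection, at the end of the existing 1-hour observation, and during the Cycle 1 Day 1 overnight stay. In Phase I, also record them at the existing 2, 4, 6 and 24 h draws on Cycle 1 Day 1 and Cycle 2 Day 15.

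**Cost.** Amendment text and a pulse-oximetry reading with respiration rate, which is already a required vital sign, at times when the patient is on site. The Cycle 1 Day 2 return for the 24 h sample is already required by Section 5.1.2. No new visit, longer stay, invasive procedure or dose change is needed. The downside is some incidental low readings to assess.

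**Limits.** In primed cohorts the first full dose on Day 8 would get only the pre-dose and 1-hour readings, so the 3 to 6 h window after it stays uncovered. Phase IIA has no cytokine draws and would get only the pre-dose, 1-hour and overnight readings.

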1.6 RATIONALE FOR THE STUDY

Cancer progression is frequently associated with genetic changes and abnormalities - including mutations in Wnt, p53, AKT, and signal transducer and activator of transcription 3 (STAT3) – which suppress transcription of critical cytokines, leading, in turn, to immunosuppressive tumor microenvironments. It is hypothesized here that administration of the cGAMP analog IMSA101 (either as monotherapy or in combination) can bypass immunosuppressive factors through the direct stimulation of dendritic cells (DCs). Preliminary mouse experiments suggest that IMSA101-mediated stimulation can super-activate residual DCs through the increased expression and secretion of CD86, interferon β , and cross-present antigens to CD8+ T cells. This approach is designed, in effect, to transform "cold" IO non-responding tumor cells into "hot" IO sensitive cells, addressing unmet medical need and achieving clinical benefit through intensified immuno-modulation of malignant cells.

2 STUDY OBJECTIVES AND ENDPOINTS

2.1 PRIMARY OBJECTIVE

• Establish safe recommended Phase II doses (RP2Ds) of IMSA101 administered as monotherapy or in combination with an ICI

2.2 SECONDARY OBJECTIVES

- Characterize the safety and tolerability of IMSA101 administered to cancer patients via intratumoral injections as monotherapy or in combination
- Identify and characterize preliminary signals of anti-tumor activity including overall response rate (ORR), duration of treatment response (DOR), time-to-tumor progression (TTP), and progression-free survival time (PFS)
- Characterize the PK of IMSA101 administered by intratumoral injection as monotherapy

2.3 EXPLORATORY OBJECTIVES

• Assess the PD and biologic activity of IMSA101

2.4 STUDY ENDPOINTS

2.4.1 **Primary Endpoint**

• Maximum tolerated dose (MTD)/RP2D of IMSA101 administered by intratumoral injection alone or in combination with approved ICI therapy

2.4.2 Secondary (Safety) Endpoints

- Safety of IMSA101 as determined by incidence of treatment-emergent AEs (TEAEs), laboratory abnormalities, and other safety using Common Terminology Criteria for Adverse Events (CTCAE) v5.0 criteria
- Incidence of dose limiting toxicities (DLTs) in patients administered IMSA101 by intratumoral injection

2.4.3 Secondary (Efficacy) Endpoints

Secondary efficacy endpoints may include:

- Response evaluation criteria in solid tumors (RECIST)-based objective response rate (ORR)
- Duration of response (DOR)
- Time to RECIST-based tumor progression (TTP)
- Progression-free survival time (PFS)

2.4.4 Pharmacokinetic Endpoints (Phase I Monotherapy only)

• PK parameters of IMSA101 administered by intratumoral injection:

Cycle 1 Day 1: Pre-Dose, 10 min, 20 min, 30 min, 1 h, 2 h, 4 h post-dose

Cycle 2 Day 15 (if any detectable signal noted in Cycle 1):

Pre-Dose, 10 min, 20 min, 30 min, 1 h, 2 h, 4 h post-dose. Additionally, 6 h, 24 h post-dose if previous 4 h post-dose measurement was found detectable in Cycle 1

2.4.5 **Exploratory Pharmacodynamic Endpoints (Phase I only)**

- Blood levels of cytokines (pre-dose, 2h, 4h, 6h, 24 h post-dosing Cycle 1 Day 1 and Cycle 2 Day 15): IL6 and IP10, IFNγ, TNFα, IL-10, IL-1β, IFN-β, MCP-1 (CCL2)
- Blood (pre-dose on Day 1 of Cycles 1, 2, and 3): Flow cytometry of Cryopreserved PBMCs CD3, CD4, CD8, CD45, CD69, CD19, CD56, FOXP3, PD-1, PD-L1, CD141, CD86, HLA-DR, CD14, CD16, CD11c
- Tumor Biopsy for injected tumor and non-injected tumor, if applicable (non-injected tumor biopsy required in at least 1 patient per cohort) (pre-dose on Cycle 1 Day 1, Cycle 1 Day 15, Cycle 2 Day 15:) Multiplexed Immunofluorescence (mIF) including antibodies to CD45, CD4, CD8, CD11c, CD56(NK), FOXP3, DAPI, PD-1, and PD-L1

An aliquot of tumor sample for injected and non-injected tumor is to be stored for later RNA isolation and sequencing when the analysis is warranted based on clinical or immunological responses.

3 STUDY DESIGN

3.1 STUDY DESIGN OVERVIEW

This is an open-label, dose escalation (Phase I), and dose expansion (Phase IIA) study designed to evaluate safety and efficacy of IMSA101 alone or in combination with an ICI (Phase I and II). Therefore, the study will be conducted in 2 phases. The dose of IMSA101 in Phase IIA will be based on the monotherapy and combination RP2Ds from Phase I.

The following methodology applies to all patients (unless otherwise indicated):

- Pre-treatment screening radiographic tumor assessments will be collected within 30 days prior to initial dose for all patients. Photographic assessments of skin lesions will be performed as detailed in a separate photography manual.
- Treatment cycles will be 28 days in duration with lesions injected weekly on Day 1 for the first three weeks of Cycle 1 and then every 2 weeks during Cycles 2 and beyond.
- A single pre-defined lesion/lesion site (longest diameter ≥ 10 mm and ≤ 50 mm) shall be injected throughout study duration, if possible. Where the original injection site is considered by the investigator to become inaccessible, a second lesion/lesion site shall be selected as a replacement and this shall be used henceforth so long as it is considered accessible. Subsequent injection sites shall be replaced when they are considered inaccessible.
- Where no remaining accessible lesions are present and where benefit of IMSA101 therapy is, in the opinion of the investigator, being derived by the patient, continued injections of IMSA101 into the vicinity of an inaccessible lesion or, in the case that a lesion can no longer be radiographically visualized, into the last known location of the non-visible lesion shall be allowed.
- Patients will be admitted to the hospital for observation overnight following intratumoral injection with IMSA101 on Day 1 of Cycle 1. Patients will be followed throughout the study for drug tolerability and safety by collection of clinical and laboratory data, including information on adverse events (AEs) using CTCAE v5.0 criteria, serious AEs (SAEs), DLTs, concomitant medications, vital signs, and ECGs.
- Patients will be assessed for anti-tumor efficacy based on radiographic assessments and if applicable, photographic tumor assessments, and analysis of ORR, DOR, TTP, and PFS using RECIST v1.1 criteria (Appendix 13.2) at screening and the end (≤ 7 days) of even numbered cycles (Cycle 2, Cycle 4, etc.) after the first dosing.

RECIST v1.1 criteria do not mention including or excluding lesions that are being biopsied or injected. However, for the purposes of this protocol, the injected and biopsied lesions are to be captured as non-target lesions only (Phase I only), as follows:

- Injected and biopsied lesion = non-target lesion #1
- Non-injected and biopsied lesion = non-target lesion #2 (if applicable)

See Schedule of Assessments and Study Activities (Table 1 and Table 2) for details.

3.1.1 **Phase I – Dose Escalation Plan**

The Phase I dose escalation is illustrated in Figure 8 for monotherapy and Figure 9 and Figure 10

for combination therapy.

Phase I Dose Escalation – Monotherapy:

- Each dose escalation cohort will initially recruit at least 3 patients in a standard 3+3 design. To proactively ensure at least 3 patients are considered evaluable, a fourth patient may be enrolled and treated in addition to the initial 3 patients in each cohort (the fourth patient may only be enrolled if they are identified at the time the third patient slot is being filled).
- Dose escalation design in which administered dose levels will be escalated stepwise in successive cohorts of 3 to 6 (NOTE: 7 if fourth slot is filled and a single DLT is identified among the first 4 patients) patients per dose group until the RP2D or MTD level is identified.
- The first patient enrolled in each dose level must complete the first two weeks of Cycle 1 prior to enrolling the second and third (fourth when applicable) patients.
- Dose levels to be evaluated include (although not necessarily limited to) 100 µg (representing 1/60th of the pre-clinical HNSTD dose), 200 µg, 400 µg, 800 µg, and 1,200 µg.
- IMSA101 will initially be administered by intratumoral injections on Day 1 of Weeks 1, 2, and 3 for Cycle 1 (i.e., weekly dosing 3 out of 4 weeks), and on Day 1 of Weeks 1 and 3 (i.e., bi-weekly dosing) for all cycles thereafter.
- No dose escalation decisions will be made until all patients in a dose level complete the first 28 days of treatment. NOTE: this includes a fourth additional patient when applicable. Dose-escalation/de-escalation decisions will be based on the occurrence of DLTs during Cycle 1 of the evaluated dose level and the recommendation of the Cohort Review Committee (CRC).
- If no DLTs are observed among the initial 3 (4 when applicable) patients of an evaluated dose level, the dose will be escalated for the following 3 patients.
- If a single DLT occurs among the initial 3 (4 when applicable) patients of an evaluated dose level, 3 additional patients will be enrolled at the same dose level.
- If ≥ 2 DLTs occur among the initial 3 (4 when applicable) or 6 (7 when applicable) patients in an evaluated dose level, the dose level shall be considered unacceptably toxic and escalation will be discontinued.
- Subsequent to invalidation of a given cohort (e.g., when ≥ 2/3 [4 when applicable] or ≥ 2/6 [7 when applicable] patients in an evaluated dose level experience a DLT), a new cohort (e.g., dosing Cohort Xa) will be evaluated in which IMSA101 will be administered by intratumoral injection at the same dose level but with the Day 1 dose (priming dose) reduced to the next lower dose level.
- For dosing Cohort Xa, if ≥ 2/3 (4 when applicable) or ≥ 2/6 (7 when applicable) patients experience a DLT, the amended dose level shall be considered unacceptably toxic and the next lower dose (DL-1) level shall be provisionally labeled the MTD.

- If the amended dose level Xa is found to be safe, dose escalation shall proceed with the exception of the priming dose (Cycle 1, dose 1) which shall be held constant and not escalated further.
- No fewer than 6 total patients shall be evaluated at a given dose level prior to confirmation of the dose level as the MTD or RP2D.

Phase I Dose Escalation - Combination Therapy:

- Combination therapy with IMSA101 + ICI includes the following IMSA101 dose levels:
 - 800 µg
 - 1,200 μg
 - 2,400 µg (with an initial "priming" dose of 1,200 µg)
 - 3,600 µg (with an initial "priming" dose of 2,400 µg)
 - 4,800 μg (with an initial "priming" dose of 3,600 μg)
- Combination dosing of IMSA101 shall be evaluated in Phase I upon satisfaction of the following criteria:
 - A. A given dose level (combo dose level 1) has been confirmed as safe for monotherapy dosing (i.e., < 2/6 [7 when applicable] patients experience Cycle 1 DLT).
 - B. The next higher dose level (combo dose level 2) has been confirmed as safe for monotherapy dosing (i.e., < 2/6 [7 when applicable] patients experience Cycle 1 DLT).
 - C. The dose level (combo dose level 1) is found to demonstrate adequate IMSA101 PD activity based on exploratory endpoints.
- Eligible patients for Phase I combination dosing shall meet one of the following criteria:
 - have radiographically-confirmed RECIST stable disease through ≥ 2 consecutive cycles of an approved PD-1/PD-L1-targeted immune checkpoint inhibitor (ICI) administered as monotherapy
 - be clinically stable following a first (unconfirmed) follow-up radiographic scan demonstrating progression of disease on ICI monotherapy
 - have progression through prior ICI therapy administered either as mono or combination therapy
 - have received no prior ICI therapy but otherwise be ineligible for all available standards of care
- Phase I combo patients have experienced no prior Grade ≥ 3 CTCAE adverse events on ICI therapy that were considered by the investigator to be at least possibly ICI drug-related
- Phase I combo patients shall either receive de novo the combination of IMSA101 + an ICI of their investigator's choosing or, in cases where they are already receiving ICI monotherapy,

have IMSA101 added to their current therapy such that Day 1 of IMSA101 shall represent Cycle 1, Day 1.

- A radiographic tumor assessment shall have occurred within 30 prior days of adding IMSA101 to current therapy.
- Phase I combination therapy IMSA101 doses of 800 µg and 1,200 µg will be administered by intratumoral injections each week for 3 weeks in Cycle 1 (Days 1, 8, and 15), and for Cycle 2 and all other cycles thereafter, every other week on Days 1 and 15. Additional combination therapy IMSA101 doses of 2,400 µg, 3,600 µg, and 4,800 µg require the following priming dose on Day 1 of Cycle 1: 1,200 µg for the 2,400 µg dose group, 2,400 µg for the 3,600 µg dose group, and 3,600 µg for the 4,800 µg group. After Day 1 of Cycle 1, the full dose for these groups will be administered on Day 1 of Weeks 2 and 3 of Cycle 1 (i.e., weekly dosing 3 out of 4 weeks), and on Day 1 of Weeks 1 and 3 for all cycles thereafter (i.e., bi-weekly dosing).
- Safety evaluations and dose escalation of IMSA101 administered in combination with current ICI therapy shall proceed in a manner consistent with monotherapy escalation, with the exception of allowed de-escalation, and shall proceed independently of monotherapy dose escalation and evaluations.
- De-escalation: If ≥ 2 DLTs occur among the initial 3 (4 when applicable) or 6 (7 when applicable) patients, de-escalation of IMSA101 is allowed for the combination therapy dose levels as follows:
 - 2,400 μg may be de-escalated to 1,800 μg (with a priming dose of 1,200 μg on Day 1 of Cycle 1)
 - 3,600 μg may be de-escalated to 3,000 μg (with a priming dose of 2,400 μg on Day 1 of Cycle 1)
 - 4,800 μg may be de-escalated to 4,200 μg (with a priming dose of 3,600 μg on Day 1 of Cycle 1)

If \geq 2 DLTs occur among the initial 3 (4 when applicable) or 6 (7 when applicable) patients at a de-escalated dose level, the dose level shall be considered unacceptably toxic and escalation will be discontinued.

- Administration of combination drug will follow the labeled instructions for the product.
- IMSA101 dose escalation shall proceed such that there will be generated separate RP2Ds for IMSA101 administered alone or in combination with other agents (although it is possible these will be the same).
- No fewer than 6 total patients shall be evaluated at a given dose level prior to confirmation of the dose level as the MTD or RP2D.

[figure not shown]

Figure 8 Phase I Dose Escalation for Monotherapy

- ¹ Each dose escalation cohort will initially recruit at least 3 patients in a standard 3+3 design. To proactively ensure at least 3 patients are considered evaluable, a fourth patient may be enrolled and treated in addition to the initial 3 patients in each cohort (the fourth patient may only be enrolled if they are identified at the time the third patient slot is being filled).
- ² Combination dosing and escalation will lead to separate RP2Ds for IMSA101 administered alone or in combination with other agents (although it is possible these will be the same).

[figure not shown]
[figure not shown]

[figure not shown]
Figure 9 Phase I Dose Escalation for Combination Therapy Doses 800 or 1,200 µg

DLT: dose limiting toxicity; RP2D: Recommended Phase II dose

*MTD = one dose lower than discontinued dose

- ¹ Each dose escalation cohort will initially recruit at least 3 patients in a standard 3+3 design. To proactively ensure at least 3 patients are considered evaluable, a fourth patient may be enrolled and treated in addition to the initial 3 patients in each cohort (the fourth patient may only be enrolled if they are identified at the time the third patient slot is being filled).
- ² Combination dosing and escalation will lead to separate RP2Ds for IMSA101 administered alone or in combination with other agents (although it is possible these will be the same).

C1D1: Cycle 1, Day 1; DLT: dose limiting toxicity; RP2D: Recommended Phase II dose

*MTD = one dose lower than discontinued dose

- ¹ IMSA101 given on Days 1, 8, and 15 (Cycle 1) and bi-weekly thereafter. ICI therapy administered according to product instructions.
- ² Each cohort will initially recruit at least 3 patients in a standard 3+3 design. To proactively ensure at least 3 patients are considered evaluable, a fourth patient may be enrolled and treated in addition to the initial 3 patients in each cohort (the fourth patient may only be enrolled if they are identified at the time the third patient slot is being filled). The first patient enrolled in each dose level must complete the first two weeks of Cycle 1 prior to enrolling the second and third (fourth when applicable) patients.
- ³ Combination dosing and escalation will lead to separate RP2Ds for IMSA101 administered alone or in combination with other agents (although it is possible these will be the same).

[figure not shown]
3.1.2 **Phase IIA – Dose Expansion Plan**

The Phase IIA dose expansion is illustrated in Figure 11.

- This dose-expansion stage is intended to confirm the tolerability of the RP2D and identify provocative signals of IMSA101 anti-tumor activity.
- It is anticipated that the monotherapy and combination RP2Ds will be evaluated in 3 discrete arms of 20 patients each with a single arm evaluating monotherapy (Arm A) and 2 arms evaluating IMSA101 in combination with IO therapies (Arm B and Arm C).
 - Arm B will be a combination of IMSA101 with PD-1/PD-L1-targeted ICIs. Dosing will be predicated by the combination RP2D identified in Phase I.
 - Arm C will be a combination of IMSA101 with non-PD-1/PD-L1-targeted immunooncology drugs approved by the Food and Drug Administration (FDA).
- Administration of approved drugs to be combined with IMSA101 will follow the labeled instructions for the product.
- Combination arms evaluating IMSA101 combinations shall include a safety run-in of 5-10 patients to be conducted as follows:
 - If \leq 1 of 5 initial safety evaluable patients experience a DLT during Cycle 1, enrollment shall proceed to Patient 6.
 - If \leq 3 of 10 initial safety evaluable patients experience a DLT during Cycle 1, enrollment shall proceed to its entirety (20 patients in that arm).
 - If ≥ 2 of 5 or ≥ 4 of 10 patients experience a DLT, dose de-escalation shall occur to the next lower dose level evaluated in Phase I and the run-in shall be repeated at the next lower dose.
